Aim 1. To determine the effect of Allopurinol treatment on GFR of hyperuricemic pediatric CKD patients. In a randomized controlled study, pediatric CKD patients with hyperuricemia (serum UA ≥ 5.5 mg/dL) will be allocated 2:1 to Allopurinol versus standard of care (SOC) control for 6 months. Participants will be stratified into two cohorts by disease etiology (cohort A: non-glomerular, cohort B: glomerular). Equal allocation of race is expected as our local population is composed of 50% black race. The primary outcome measure is the amount of GFR change from baseline to 6 months compared to the control group in both cohorts. Secondary outcomes are measurement of the amount of UA and BP change from baseline to 6 months.

Aim 2. Establish whether Allopurinol treatment reduces Nlrp3 inflammasome and renal injury biomarkers. In this exploratory aim, urine and serum biomarkers of Nlrp3 inflammasome activation (hs-CRP, XO enzyme activity, Nlrp3, IL-1 β , IL-18) and renal injury (KIM-1, ET-1, NAG, and NGAL) will be collected at 3 and 6 months and compared to baseline of cohorts A and B treatment and control groups.

Impact: GFR change from baseline to 6 months by treatment and cohort will be used to directly inform the effect size and sample size calculations required for a randomized controlled multicenter pediatric intervention trial. The simultaneous and novel exploration of the effect of XO inhibition on inflammation and renal injury biomarkers will provide crucial data that may identify mechanism of the XO inhibition effect.

BACKGROUND AND SIGNIFICANCE

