Pediatric CKD epidemiology is different from adult CKD in the following ways. First, the etiology is primarily due to non-glomerular diseases (e.g. congenital anomalies of the kidney and urinary tract [CAKUT], the most common cause at 50%), and glomerular diseases (e.g. acute glomerulonephritis) rather than the primary adult causes of diabetes and hypertension. CAKUT conditions and the resultant, often insidiously progressive, CKD is present from birth. Whereas the typical age of onset of glomerulonephritis is the teenage years with acute onset renal dysfunction leading often to a more rapid chronic progressive disease than non-glomerular CKD. In pediatrics, factors that affect the rate of renal function decline and lead to a faster progression of CKD towards end stage renal disease (ESRD) are black race, glomerular disease etiology, and modifiable disease phenotypes of hypertension, proteinuria, and hyperuricemia [2, 4].

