Results from adult clinical trials are often extrapolated to the pediatric population, but with the above listed differences in CKD epidemiology, the beneficial effect of UA lowering therapy should be tested separately in pediatrics. The effect of UA lowering therapy may differ for those with glomerular versus non-glomerular disease etiology, race, or for those with proteinuria versus none. There are data to support a similar beneficial effect from XO inhibitors in pediatrics as in adults, but the effect modification, if any, of these factors is not specifically known. For example, a single randomized placebo-controlled pediatric CKD trial of Allopurinol for 4 months demonstrated a statistically significant increase in the mean glomerular filtration rate (GFR) from baseline to endpoint of +16 ml/min/1.73m² (SD=9.3). However, this study did not report race, did not stratify participants by glomerular or non-glomerular disease etiology or presence of proteinuria, and did not use intention to treat principles when those with a pre-specified adherence rate <80% were excluded at the end of the study, leading to an overall study power of 78%. The reported rate of GFR change in adult trials range from approximately +1 to +3 ml/min/1.73m² (SD=1-3) [20]. While we recognize results in pediatric populations may differ from adults, further confirmation is needed before progressing to large scale trials. A feasibility pilot clinical trial proposed here will test the effect of XO inhibition on GFR using study design principles of blocked allocation of participants to control for known factors that affect GFR decline.

RESEARCH METHODS – Study Design

Specific Aim 1. To determine the effect of Allopurinol treatment on GFR of pediatric CKD patients with hyperuricemia.

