1.1. Rationale and Objective: While there is support in the literature for beneficial effect of XO inhibitor therapy on GFR and BP in pediatric CKD, the degree of expected change in GFR based on disease etiology is uncertain. Therefore, we propose a randomized controlled trial of hyperuricemic pediatric CKD participants in a 2:1 allocation between Allopurinol and standard of care (SOC) therapy, and stratified by disease etiology (cohort A: non-glomerular, cohort B: glomerular). Randomization procedure will be blinded, but the allocation will be unblinded to investigator and participant because of the lack of placebo. Allopurinol will be titrated to reach a normal range of serum UA 3-5 mg/dL by 6 months. Local SOC practice for pediatric CKD includes control of blood pressure with anti-hypertensives, control of acidosis, control of proteinuria, and frequent laboratory monitoring to measure the rate of renal function decline. The primary outcome of Aim 1A is change in GFR between baseline and 6 months by treatment group. The secondary outcomes are change in serum UA, and change in BP over the same time. An exploratory sub-aim (Aim 1B) will identify and compare GFR change by cohort characteristics (disease etiology, proteinuria, and race) that may influence future trial designs.

1.2. Experimental Design (Table 1): We will conduct a 6-month randomized treatment (Allopurinol) vs. SOC clinical trial to measure change in GFR over time in pediatric hyperuricemic CKD participants. We will conduct this study after obtaining appropriate consent and assent. Our recruitment pool will include all patients receiving medical care from the CHoR Pediatric Nephrology Division, new and recurring outpatient encounters. The division currently sees approximately 3,500 outpatient encounters per year. The study visits will coincide with SOC visits with the possible exception of visit V1A (some but not all participants will normally be seen for SOC 1 month after the baseline visit). The following inclusion and exclusion criteria apply:

- Inclusion Criteria: CKD stage 1-5; Age 2-20 years old at time of enrollment; Hyperuricemic
- Exclusion Criteria: Contraindication to Allopurinol; Elevated baseline liver function tests; Receiving acute or chronic dialysis; Primary metabolic disorder; Sickle cell disease; Autosomal Dominant Polycystic Kidney Disease; Cystinosis; Bartter or Gitelman Disease; Pregnant or nursing.

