1.3. Statistical Analysis: We will report means/medians and standard deviations (SD)/interquartile range (IQR) for all continuous measures, and frequency and proportions for categorical variables. Assuming a clinically significant difference between treatment groups of 3 ml/min/1.73m² and individual group SDs=3.5, a one-sided analysis t-test performed at $\alpha=0.05$ will achieve at least 80% power for a sample size of 42 if the participants will be allocated in a 2:1 ratio between treatment and control. We will also enroll participants into two cohorts to assure proportional distribution between non-glomerular (cohort A) and glomerular (cohort B) disease etiology. Our local pediatric CKD population composition by disease etiology is similar to national proportions of approximately 70% non-glomerular and 30% glomerular disease etiology. We will therefore over-sample the glomerular sub-population in cohort B and limit enrollment of the non-glomerular cohort A to n=19, maintaining roughly a 2:1 proportion. The goal allocation enrollment by treatment group and cohort size is summarized in **Table 2**. Two-sample t-tests on the GFR change score will be used to address Specific Aim 1A while separate 2-way ANOVA models with an interaction will be used to address Aim 1B. Repeated measures ANOVA models will be used to inform from all three time points in an intent-to-treat fashion.

Table 2: Goal allocation enrollment

Treatment Group	Allopurinol Group	Control Standard of Care Group
Cohort A: Non-glomerular disease etiology	19	7
Cohort B: Glomerular disease etiology	9	7
Total	28	14

Specific Aim 2. Determine the effect of Allopurinol treatment on Nlrp3 inflammasome and renal injury biomarkers.

2.1. Rationale and Objective: To our knowledge there are no studies that explore the effect of XO inhibition on the known mechanism of hyperuricemia induced Nlrp3 inflammasome activation and renal injury in a clinical trial setting. We therefore propose to establish whether XO inhibition reduces levels of these biomarkers at 3 and 6 months compared to baseline. If our hypothesis is correct that inflammasome-mediated renal injury is improved by Allopurinol, we expect to find that after 3 and 6 months of Allopurinol treatment, the biomarker levels will be reduced from baseline in both treated cohort groups compared to control participants.

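### On the natural reading, the Aim 1B race and proteinuria models leave out the etiology stratum, so part of an etiology effect can be credited to either factor if it overlaps with etiology

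*Combined protocol and SAP*

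**What the plan says.** Section 1.3 (Statistical Analysis) states that "separate 2-way ANOVA models with an interaction will be used to address Aim 1B". It does not say which two factors enter each model. Section 1.1 describes Aim 1B as an exploratory sub-aim that "will identify and compare GFR change by cohort characteristics (disease etiology, proteinuria, and race) that may influence future trial designs". Background and Significance gives the reason: "The effect of UA lowering therapy may differ for those with glomerular versus non-glomerular disease etiology, race, or for those with proteinuria versus none". Read together, these point to three models, each crossing treatment with one characteristic.

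Etiology has a special place in the design. Aim 1 and Section 1.1 make it the stratification factor (cohort A non-glomerular, cohort B glomerular). Background and Significance lists the drivers of faster progression as "black race, glomerular disease etiology, and modifiable disease phenotypes of hypertension, proteinuria, and hyperuricemia". No section describes adjusting any analysis for cohort. On how race relates to etiology there is only an overall figure under Aim 1: "Equal allocation of race is expected as our local population is composed of 50% black race". On how proteinuria relates to etiology there is no figure.

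**The concern.** A two-way model that holds treatment and race, or treatment and proteinuria, has no place for etiology. If a factor is more common in one cohort, the two levels of that factor differ in their share of glomerular disease. An etiology effect then shows up under the factor's name in one of two ways:

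- If etiology shifts GFR change in both arms, the factor gets a false main effect.
- If etiology alters the drug effect, the factor gets a false interaction with treatment.

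Section 1.1 asks for GFR change to be compared by characteristic, so both quantities matter. The purpose of Aim 1B is to tell the next trial which characteristics to design around. Crediting an effect to the wrong one defeats that purpose.

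**Working it through.** **Inputs from the documents.** Table 2 cells are 19 non-glomerular and 9 glomerular on allopurinol, and 7 and 7 on control. Section 1.3 gives an SD of 3.5, N = 42 at 2:1, one-sided alpha 0.05, and a "clinically significant difference between treatment groups of 3 ml/min/1.73m²".

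**Inputs assumed.** The etiology effect is −3 ml/min/1.73m², and the tested factor has no true effect. Factor prevalence, glomerular v non-glomerular, is 65% v 40%, 80% v 40% or 80% v 20%. The SD of 3.5 is taken as the spread within cohort. A 3-unit cohort gap would make the arm SD about 3.8, since √(12.25 + 9 × 0.32 × 0.68) ≈ 3.8. That affects precision but not bias.

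**The plan's own figure.** SE = 3.5 × √(1/28 + 1/14) = 1.146, and 3/1.146 = 2.62. Normal-approximation power is Φ(2.62 − 1.645) = 83.5%, and the exact noncentral t gives 82.4%. The stated power of at least 80% reproduces. No figure is given for Aim 1B.

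**Precision of an Aim 1B interaction.** For a 50:50 factor spread evenly over the arms, SE = 3.5 × √(1/14 + 1/14 + 1/7 + 1/7) = 2.29. Power for a true interaction of 3 (two-sided 5%) is about 25%. Reaching 80% power needs about 2.29 × (2.02 + 0.85) = 6.6.

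**Bias by hand.** Within an arm with nG glomerular and nN non-glomerular patients, and prevalences pG and pN, the difference in glomerular share between factor levels is

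d = nG·pG/(nG·pG + nN·pN) − nG(1−pG)/(nG(1−pG) + nN(1−pN)).

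- Etiology changes only the drug effect, by −3: false interaction ≈ −3 × d in the allopurinol arm.
- Etiology shifts GFR change by −3 in both arms: false factor main effect ≈ −3 × d, from the control arm or averaged over arms, depending on coding.

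| Prevalence | d, allopurinol | d, control | False interaction | False main effect (control arm / arm average) |
|---|---|---|---|---|
| 65% v 40% | 5.85/13.45 − 3.15/14.55 = 0.218 | 4.55/7.35 − 2.45/6.65 = 0.251 | −0.66 | −0.75 / −0.70 |
| 80% v 40% | 7.2/14.8 − 1.8/13.2 = 0.350 | 5.6/8.4 − 1.4/5.6 = 0.417 | −1.05 | −1.25 / −1.15 |
| 80% v 20% | 7.2/11.0 − 1.8/17.0 = 0.549 | 5.6/7.0 − 1.4/7.0 = 0.600 | −1.65 | −1.80 / −1.72 |

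**Simulation on the Table 2 cells (3,000 trials per scenario).** The false interaction is about −0.6 to −1.6 and the false main effect about −0.8 to −1.9, close to the hand figures. The two-sided 5% interaction test rejects at most about 10% of the time. A separate run over wider splits (4,000 trials each) found the main-effect test rejecting in 27% of trials at 90% v 30%.

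**No overlap (50% v 50%).** Average bias is nil and rejection is 4–6%. Adding cohort moves the interaction SE from 2.34 to 2.38 if etiology does nothing, and from 2.55 to 2.38 if it shifts GFR change by −3.

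**What each addition does.** Adding cohort removes the false main effect when etiology is only prognostic. It does not remove a false interaction. In a check of 5,000 trials per scenario, with etiology changing only the drug effect, the cohort-only model left a false interaction of −0.8 (65% v 40%) to −1.9 (80% v 20%), with rejection up to 12%. Adding treatment by cohort as well brings the false interaction to within about 0.1 of zero and rejection to about 5%.

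**The case against.** **The omission is inferred.** Section 1.3 names no factors, so what is documented is a gap in specification. The inference is well supported by Section 1.1 and Background and Significance, but it remains an inference. One of the three models would contain etiology.

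**The overlap and the etiology effect are assumed.** A reader might infer that Aim 1B will credit an etiology effect to race. The documents do not support that. They give about 50% black overall and no split by etiology, and with no association the average bias is nil. Chance overlap in 42 patients (SD about 0.15 in glomerular share) adds noise but does not raise the average false-positive rate.

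**The harm is small beside the noise.** A bias of 0.6 to 1.6 compares with an interaction SE of about 2.4, and power for a true interaction of 3 is about 25%. Low power limits Aim 1B at least as much. This stands. It also makes the estimates and their intervals the useful output, and the estimates are what the omission biases.

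**The full model is not simply better.** A reader might infer that the model with treatment by cohort should replace the two-way models. At 80% v 20% the root mean squared error of the interaction is 2.90 without etiology and 3.24 with the full model. If etiology does nothing, it is 2.36 against 3.24, and power for a true interaction of −3 falls from 23% to 16%. This stands, and is why the fuller model belongs beside the other and not in its place.

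**The problem also runs the other way.** The treatment-by-etiology model omits race and proteinuria, and those two are not adjusted for each other. This also stands. The fuller models answer it only in part, by giving treatment by cohort adjusted for one factor at a time.

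**Conclusion.** The point holds in a limited form. On the natural reading, two of the three Aim 1B models leave out the factor by which the trial is stratified. Given an assumed 3-unit etiology effect and the assumed overlaps, a factor with no effect of its own can show a main effect or an interaction of roughly a fifth to three-fifths of that size. Inflation of the interaction test is modest. The claim is that an effect can be misattributed, not that it will be.

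A reader might also infer that the primary result is at risk. It is not: Aim 1A is a separate two-sample t-test, and nothing in the Aim 1B models changes it. Because Aim 1B is exploratory and has low power under either model, the severity is minor to moderate.

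**What to change.** In Section 1.3:

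1. Name the factors in each Aim 1B model. Keep treatment by cohort for etiology.
2. For race and for proteinuria, fit GFR change = treatment + cohort + factor + treatment × factor.
3. Report beside each the same model with treatment × cohort added. The cohort-only model does not protect the interaction, so it should not be read alone.
4. Give every interaction estimate with its confidence interval, and cross-tabulate etiology by race and by proteinuria.
5. State that where the two models disagree, Aim 1B cannot say which factor modifies the drug effect.

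The change is to analysis wording only, since etiology is already collected at baseline (Section 1.2). Residual degrees of freedom fall from 38 to 37 with cohort and to 36 with treatment × cohort. Under strong overlap the fuller model's interval widens (interaction SE about 2.4 to 3.1 at 80% v 20%). There it removes bias but does not lower overall error.

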This randomized controlled trial aims to test the hypotheses that treatment of hyperuricemia with a xanthine oxidase inhibitor (Allopurinol) reduces the rate of decline of kidney function in chronic kidney disease, and markers of renal injury and inflammation. The Data and Safety Monitoring Plan (DSMP) is outlined below. During this study, all data collected will be kept confidential in an encrypted database using identification codes. Only approved research team members will have access to the database. The study staff will review all data collection forms on an ongoing basis for data completeness and accuracy as well as protocol compliance. Reviews of subject accrual, including compliance with protocol enrollment criteria and adherence data, will be performed by the PI and study staff on a monthly basis.

Data on adherence to the treatment protocol will be collected on an ongoing basis by research staff and reviewed quarterly by the PI. Adherence of participants will be evaluated by performing pill counts at study visits and by a validated visual analogue scale of adherence (patient self-report) at the end of study visit. An intention to treat protocol is applied to this study. However, if adherence falls below a rate of 75% which might inhibit the ability of the study to test its primary hypotheses, the study investigators and statistician will convene to discuss methods for improving adherence.

The PI will designate an Independent Monitor to perform an independent review of ongoing study progress and safety. The Independent Monitor will not be a part of the key research personnel, and will be qualified to review the patient safety data. Progress reports, including patient recruitment, retention/attrition of the study as a whole as well as retention of subjects undergoing washout or conversion therapy to study initiation, and adverse events (AE), will be provided to the Independent Monitor every 6 months. The reports will be generated only from aggregate for the entire study population. A closed safety report with masked group assignment will be generated for the Independent Monitor by an unmasked member of the study team (research coordinator).

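### Intention to treat is claimed with no missing-data method, so the Aim 1A t-test is in effect a completer analysis that arm-dependent loss could bias in either direction

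*Combined protocol and SAP*

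**What the plan says.** The combined protocol and SAP defines the primary outcome (section 1.1) as the change in GFR from baseline to 6 months by treatment group. Section 1.3 states "Two-sample t-tests on the GFR change score will be used to address Specific Aim 1A", and adds "Repeated measures ANOVA models will be used to inform from all three time points in an intent-to-treat fashion". The Data and Safety Monitoring Plan says, in its paragraph on adherence, "An intention to treat protocol is applied to this study".

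The sample size in section 1.3 rests on "a one-sided analysis t-test performed at" alpha 0.05, a difference of 3 ml/min/1.73m² and "individual group SDs=3.5". The plan claims that this design "will achieve at least 80% power for a sample size of 42". Two participants go to Allopurinol for each control, and Table 2 gives 28 and 14.

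The GFR laboratory work is scheduled at baseline, 3 and 6 months in both arms (section 1.2, Table 1).

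The documents contain no definition of the analysis set, no imputation rule, no sensitivity analysis and no allowance for dropout. They do not say whether a month-6 GFR is sought after someone withdraws, or how the repeated measures ANOVA is to be estimated.

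**The concern.** Intention to treat needs two things: participants analysed in the arm to which they were randomized, and a stated way of handling those whose outcome is missing. The plan supplies only the first. A change-score t-test with no imputation rule leaves out anyone without a month-6 GFR, including those whose month-3 GFR was measured. The method that the plan itself labels intent-to-treat, repeated measures ANOVA, deletes anyone with a missed visit in its classical form.

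Loss that differs by arm is plausible. Allocation is open label, and controls have no month-1 visit (Table 1). The sponsor also expects some attrition: retention is monitored, dropout reasons are reported, and poor retention is a listed reason to stop the study. If those who leave have a different GFR course, and leave at different rates by arm, the completer comparison is distorted. The impact statement under Specific Aims says the result will feed the effect size and sample size of a multicenter trial, so an error would carry forward.

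**Working it through.** **1. The plan's own figure.** Inputs from section 1.3: difference 3, SD 3.5, one-sided alpha 0.05, 28 and 14. Noncentrality = 3 / (3.5 × √(1/28 + 1/14)) = 3 / 1.146 = 2.619. The critical t on 40 df is 1.684, giving exact power of 82.4%. The stated claim of at least 80% is reproduced, on the basis that all 42 have a month-6 GFR.

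**2. Random loss, no bias.** The documents give no rate, so a range is assumed and the same formula applied.

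| With month-6 GFR | Noncentrality | Power |
|---|---|---|
| 28 + 14 | 2.619 | 82.4% |
| 26 + 13 (about 5% lost) | 2.523 | 79.7% |
| 25 + 12 (about 10% lost) | 2.441 | 77.3% |
| 22 + 11 (about 20% lost) | 2.321 | 73.4% |

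**3. Repeated measures ANOVA, only if fitted classically.** If each follow-up visit is missed independently with probability 0.10, it keeps 0.9 × 0.9 × 42 = 34 participants.

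**4. Informative loss that differs by arm.** All inputs here are assumptions except the month-6 SD of 3.5, taken from section 1.3. The SD of change at month 3 is 3.0 and the correlation is 0.6. Participants whose month-3 GFR fell by more than 2 are lost before month 6 with probability p = 0.5 on Allopurinol and 0.15 on control; all others with probability 0.05.

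For a mean month-3 change m, let z = (−2 − m)/3.0 and P = Φ(z).
- Fraction observed: O = P(1 − p) + (1 − P)(0.95).
- Upward shift of the month-3 change among completers: (p − 0.05) × 3.0 × φ(z) / O.
- Slope of month 6 on month 3: 0.6 × 3.5/3.0 = 0.70.
- Bias = 0.70 × (Allopurinol shift − control shift).

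No background decline (m = 0): P = 0.252, φ = 0.3194.
- Allopurinol: O = 0.836, shift = 0.45 × 3.0 × 0.3194/0.836 = 0.516.
- Control: O = 0.925, shift = 0.10 × 3.0 × 0.3194/0.925 = 0.104.
- Bias = 0.70 × 0.412 = **+0.29**, with 16% and 8% lost.

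Mean decline of 1 (m = −1): P = 0.369, φ = 0.3774.
- Allopurinol: O = 0.784, shift = 0.650.
- Control: O = 0.913, shift = 0.124.
- Bias = 0.70 × 0.526 = **+0.37**, with 22% and 9% lost.

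Simulated 28:14 trials with no drug effect agree, and give a one-sided error of about 8% and 9% respectively. With 0.3 in place of 0.5 on Allopurinol, the formula gives 0.12 and 0.14, and the simulated error is 6-7%.

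With the same rule in both arms and no drug effect, the two shifts are equal, so the bias is zero and the error 5%.

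If the heavier loss falls on declining controls and the true effect is 3 (1.5 at month 3), the t-test estimates 2.7 with 70% power without background decline, and 2.6 with about 65% power with a decline of 1.

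**5. What a likelihood model changes.** This is a large-sample simulation with assumed SDs of 2.8 and 3.5, correlation 0.6, and poorer change more likely to be lost. Entries are bias in the month-6 difference.

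| Lost, Allopurinol / control | Loss depends on | t-test | Likelihood model |
|---|---|---|---|
| 15% / 15% | month 3 or 6 | about 0.00 | about 0.00 |
| 20% / 10% | month 3 | +0.22 | 0.00 |
| 30% / 10% | month 3 | +0.45 | 0.00 |
| 10% / 20% | month 3 | −0.23 | 0.00 |
| 20% / 10% | month 6 | +0.38 | +0.27 |
| 30% / 10% | month 6 | +0.75 | +0.54 |
| 10% / 20% | month 6 | −0.38 | −0.27 |

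The zeros for month-3 loss follow from the assumption that loss depends only on an observed value. The month-6 rows show what the model cannot repair.

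**The case against.** The strongest reply is that the plan is silent rather than wrong. A reader might infer that section 1.3 prescribes listwise deletion. It does not: no text mentions complete cases, and using all three time points is compatible with a mixed model on every available visit. That stands for the ANOVA. It does not rescue Aim 1A, which is assigned to the t-test.

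A reader might also infer that the plan repeats the fault it finds in the earlier pediatric trial. Background and Significance says that trial "did not use intention to treat principles when those with a pre-specified adherence rate <80% were excluded at the end of the study". That fault was discarding participants for poor adherence. This plan has no adherence exclusion, so the charge of self-contradiction fails.

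Nor do the documents make an overall arm-by-time test decisive, so no criticism of such a test applies.

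The risk of loss can be overstated. Baseline, month 3 and month 6 fall at the same times in both arms, the visits largely coincide with routine care, the GFR laboratory work is standard of care, and payment comes at the last visit. A missed month-3 visit does not touch the t-test. The loss probabilities in step 4 have no support in the documents, and a milder contrast gives a bias small beside the assumed effect of 3. All of this limits the size of the concern. It does not supply a missing-data method.

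**Conclusion.** The point holds as a gap in the analysis plan. Intention to treat is claimed, no missing-data method backs it, and the primary test is in effect a completer analysis that wastes month-3 data already being collected.

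That the primary result is biased would be too strong a reading. Bias requires loss that is related to GFR course and unequal between arms, and it can go either way. Under the step 4 assumptions it is about 0.3 ml/min/1.73m² with no background decline and about 0.4 with a mean decline of 1, roughly a tenth of the assumed effect (0.29/3 = 10%, 0.37/3 = 12%), with one-sided error of 8-9%. The loss of power needs no such assumption: about 5% random loss takes exact power just below 80%.

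One related text must be reconciled. The recruitment section says both that randomization follows washout and that participants who are hyperuricemic after washout continue in a group already assigned. If groups are fixed first, withdrawals at that step are post-randomization exclusions.

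**What to change.** In section 1.3, name as the Aim 1A analysis the arm difference in change from baseline to month 6 from a likelihood-based mixed model for repeated measures. Specify REML, visit as a category, unstructured covariance and small-sample degrees of freedom. Analyse all randomized participants as randomized, including those whose only follow-up value is at month 3. Keep the completer t-test as supportive, and use the same model for the Aim 2 biomarkers.

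Add a sensitivity analysis for loss that depends on the unobserved month-6 value, for example by shifting the assumed month-6 change of those lost, separately by arm, over a stated range. State that a month-6 GFR is sought from participants who stop study treatment, and report missing values by arm and visit.

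The cost is SAP wording, standard software, a little more analysis work and reliance on a missing-at-random assumption in the main analysis. The model does not replace a dropout allowance: at an assumed 10% loss, 42/0.90 = 46.7, so 47 would have to be randomized to end with 42 month-6 values.
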